5.3 Study Population

The study population will include all patient/sperm source dyads over 18 years of age undergoing controlled ovarian hyperstimulation for IVF with ICSI using ejaculate sperm from known sperm source and having at least 6 mature oocytes retrieved.

5.3.1 Number of Participants

As this study will be randomizing oocytes, and therefore the number of participants will depend on the average number of oocytes retrieved per patient. Following power calculation, 408 oocytes are needed for randomization in order to detect a significant difference in our primary outcome. If 6 oocytes are obtained from each patient enrolled in the study, then 68 patient/sperm source dyads will be enrolled.

Based on our 2020 data, there was a total of 1,680 mature oocytes from 137 retrievals that produced 6 or more mature oocytes for ICSI insemination, from 121 different patients. The average number of mature oocytes within ICSI cycles with 6 or more mature oocytes obtained was 12 mature oocytes. Based on this data, we anticipate 138 patient cycles are needed for this study and this could include up to 138 patient/sperm source dyads.

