The study population will include patient/sperm donor dyads where all patients over 18 years of age are undergoing controlled ovarian hyperstimulation for IVF with ICSI using ejaculate sperm and having at least 6 mature oocytes retrieved. The sperm source/donor will provide informed consent for the use of their sperm sample in this research study. The relationship of the sperm source will can be the intended father, a known sperm donor in a same-sex couple or a known donor in the case of a single patient. The identity of the donor cannot be anonymous.

Number of Participants

Following power calculation, 408 oocytes will be needed to randomize (see details in the statistics section). The number of patient/sperm source dyads enrolled will depend on the number of oocytes obtained from each patient. The maximum number of subjects will be 68 (in the event that 6 oocytes were obtained from every patient enrolled in the study).

Number of Study Sites

This study will take place at NYU Langone Reproductive Specialists of NY.

Primary Outcome Variables

The primary outcome of our study is to evaluate whether good quality embryo formation is significantly improved with ICSI following sperm separation using ZyMot compared to density gradient.

Secondary and Exploratory Outcome Variables

The secondary objectives will be to evaluate:

1. Sperm parameters prior to and following sperm separation with ZyMot compared to density gradient
2. Normal fertilization rates following ICSI comparing sperm separation with ZyMot with density gradient
3. Euploid rates, in the event that PGT-A was performed, following ICSI comparing sperm separation with ZyMot with density gradient
4. Embryo transfer results including:
 - a. Not pregnant
 - b. Biochemical pregnancy, defined as BHCG value > 5 mIU/ml without ultrasound evidence of gestational sac within the uterus
 - c. Clinical miscarriage, defined as loss of a pregnancy following a positive BHCG value and ultrasound revealing presence of a gestational sac within the uterus
 - d. Clinical pregnancy, defined as positive BHCG with a gestational sac within the uterus
 - e. Ongoing Pregnancy, defined as a positive BHCG value with ultrasound evidence of intrauterine gestational sac at or past 8 weeks gestation
 - f. Live birth, defined as birth of a baby at 20 weeks or later, showing signs of life, including breathing, beating of the heart, pulsation of the umbilical cord, or definite movement of the voluntary muscles.

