6.4.2 Sample Size Considerations

For a two-tailed McNemar's test with alpha level 0.05, the following relation yields an approximate power of 80% to detect a difference d between proportions p_1 and p_2 : $n = \frac{16pq(1-r)}{d^2}$ where n is the size of the sample (i.e. number of eggs), $p = (p_1 + p_2)/2$, $q = 1 - p$, $d = |p_2 - p_1|$, and r is the phi

correlation coefficient¹. We will assume a conservative estimate for the correlation $r=0.5$. Assuming a 48% good quality blastocyst development rate and a 7% improvement in good quality blastocyst development with ZyMoT, we would need a total of 408 oocytes randomized to either density gradient or ZyMoT separation, which would equate to 68 patient/sperm source dyads each with ≥ 6 eggs retrieved.

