7.15 Study Completion

Study will be completed when 408 oocytes are randomized which is anticipated to be in approximately 1-2 years from study commencement.

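### Section 5.3.1 says 138 cycles are needed, but the 408-oocyte completion rule implies about 34 (68 at most); separately, 408 oocytes give about 52% power, not 80%

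*Combined protocol and SAP*

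**What the plan says.** Completion is defined in oocytes. Section 7.15 says "Study will be completed when 408 oocytes are randomized", and the synopsis (Study Duration) gives the same rule.

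The participant count is given in three places:

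- Synopsis, Number of Participants: "The maximum number of subjects will be 68 (in the event that 6 oocytes were obtained from every patient enrolled in the study".
- Section 6.4.2: the 408 oocytes are a number "which would equate to 68 patient/sperm source dyads", each with 6 or more eggs.
- Section 5.3.1: 408 oocytes and 68 dyads are repeated for the case of 6 oocytes per patient. The section then cites the site's 2020 data (1,680 mature oocytes from 137 retrievals with 6 or more mature oocytes for ICSI, an average of 12) and concludes that "we anticipate 138 patient cycles are needed for this study and this could include up to 138 patient/sperm source dyads".

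The only sample size calculation is in section 6.4.2. It is framed "For a two-tailed McNemar's test with alpha level 0.05", uses a formula that "yields an approximate power of 80"%, and takes n = 16pq(1-r)/d², with n described as a count of eggs and r set at 0.5. The rates enter as follows: "Assuming a 48% good quality blastocyst development rate and a 7% improvement in good quality blastocyst development with ZyMoT".

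**The concern.** A higher yield per cycle should lower the number of cycles needed. Section 5.3.1 moves from 6 oocytes per patient to an average of 12, yet its count rises from 68 to 138, twice the synopsis maximum. No second sample size, attrition allowance or derivation is given to explain the rise.

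The number of participants is what an ethics board and a reader use to judge the burden and precision of the trial. As written, section 5.3.1 leads them to expect up to 138 dyads, while the completion rule would end recruitment after about a quarter of that number.

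Checking 408 itself raises a second question. A McNemar sample size is a number of pairs, and the design splits each patient's oocytes half and half. If 408 is a number of pairs but is applied as a number of oocytes, the trial stops at half the size that its own formula requires.

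**Working it through.** **Inputs.** From section 6.4.2: two-sided alpha 0.05, power 80%, p1 = 0.48, p2 = 0.55, r = 0.5; hence p = 0.515, q = 0.485, d = 0.07. From section 5.3.1: 1,680 mature oocytes in 137 eligible retrievals, average stated as 12. From section 5.3.2: at least 6 mature oocytes.

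**1. Reproduce the plan's figures.** 16 × 0.515 × 0.485 × 0.5 / 0.07² = 407.8, so 408. (Reading the 7% as relative gives 1,771, so the plan used 7 percentage points.) 408 / 6 = 68. Both figures reproduce.

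**2. Cycles implied by the completion rule.** 1,680 / 137 = 12.26 per cycle. 408 / 12 = 34; 408 / 12.26 = 33.3, so again 34. Against this, 138 / 34 = 4.06 and 138 / 68 = 2.03. Read forwards, 138 × 12 = 1,656 oocytes, which is 4.06 times 408.

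**3. Possible sources of 138.**

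| Route | Oocytes | Cycles |
|---|---|---|
| Unpaired test, 48% v 55%, continuity-corrected: 828 per arm | 1,656 | 138.0 at 12 |
| Unpaired test, no correction: 800 per arm | 1,600 | 133.3 at 12 |
| Plan's formula with r = 0: 816 per arm | 1,632 | 136 at 12 |
| 408 read as pairs | 816 | 136 at 6; 68 at 12 |

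The first route matches exactly and uses the 12-oocyte average that section 5.3.1 cites.

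**4. What n counts in the formula.** With n pairs, the difference between two correlated proportions has variance of about 2pq(1-r)/n. Setting d equal to (1.960 + 0.842) standard errors gives n = 2 × 2.802² × pq(1-r)/d² = 15.70 pq(1-r)/d², rounded up in the plan to 16. So n is the number of pairs. As a cross-check, at r = 0 the formula gives 815.6, which is close to the ordinary unpaired size per arm (800) and about half the unpaired total (1,600).

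**5. Power at 408 oocytes.** Half and half allocation gives 204 per arm, hence at most 204 pairs.

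- r = 0.5: SE = √(2 × 0.515 × 0.485 × 0.5 / 204) = 0.0350; 0.07 / 0.0350 - 1.96 = 0.04; power about 52%. The McNemar power formula based on the discordant proportion (0.253) gives 51%.
- r = 0: SE = √(2 × 0.515 × 0.485 / 204) = 0.0495; 0.07 / 0.0495 - 1.96 = -0.55; power about 29%.
- 408 pairs (816 oocytes), r = 0.5: about 80%, the stated figure.

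**The case against.** The strongest defence is that the trial's size is not in doubt. The synopsis and section 7.15 both end the study at 408 oocytes, and sections 5.3.1 and 6.4.2 give the same requirement. The 138 is a forecast in one section, and no stopping or analysis rule uses it. The 68 is conditional on 6 oocytes per patient and agrees with 408. All of this stands, and it limits the first part of the point to one wrong figure. A reader might infer that 34, 68 and 138 conflict three ways. They do not: 34 is derived here and lies within a maximum of 68.

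Attrition could be offered as the explanation, since sections 6.3.4 and 6.3.7 let consented dyads drop out on the day of retrieval. But the 2020 data already cover only ICSI retrievals with 6 or more mature oocytes, no allowance is stated, and going from 138 to 34 would need about 75% loss (1 - 34/138). The synopsis maximum makes no distinction between consented and randomized dyads.

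A reader might also infer that the protocol rests on a second, unpaired calculation. The match in step 3 is exact, but no such calculation is documented. Other routes come within a few cycles, and at the unrounded yield of 12.26 the same 1,656 oocytes give 135 cycles. The unpaired origin is likely, not established.

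On power, it can be said that section 6.4.2 defines n as eggs and that the question would remain if the 138 sentence were deleted. The second remark is correct, and the power shortfall is therefore a separate error. The first does not help: calling n eggs does not change what the formula returns.

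**Conclusion.** Wrong as written, on two counts.

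First, the 138 cycles and dyads in section 5.3.1 do not follow from 408 oocytes at 12 per cycle. The figure is about four times the 34 that the protocol's own data imply and twice the stated maximum of 68. This needs no assumption beyond the protocol's figures and holds whatever the source of 138.

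Second, 408 oocytes do not deliver the stated 80% power. At the planned 48% against 55%, power is about 52% if the oocytes form 204 true pairs with r = 0.5, and about 29% if there is no correlation. The 52% is the best case under the plan's own r; a correlation above 0.5 would raise it, and one below would lower it towards 29%. It also assumes one-to-one pairs, which the protocol does not define.

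The documents do not support saying that an approved number of subjects is breached: this version is marked as a draft and states no approved number. Nor do they support calling the completion rule ambiguous; the rule is clear, but its size does not match the claimed power.

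**What to change.** State in section 6.4.2 whether 408 means oocytes or pairs. Then make the synopsis and sections 5.3.1, 6.4.2 and 7.15 carry the same target, expected number of dyads and maximum.

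- **If completion stays at 408 oocytes:** delete 138, state about 34 dyads expected and 68 at most, and restate the power as about 52% at best under r = 0.5. This is a change of wording with no extra recruitment; the price is a less favourable stated power.
- **If 408 pairs were intended:** the target is 816 oocytes, with about 68 cycles expected at 12 per cycle and at most 136 at 6. The completion rule and maximum must change, and recruitment doubles.
- **If the size behind 138 cycles was intended:** the target is about 1,656 oocytes, with 138 cycles expected and at most 276 (1,656 / 6). The calculation must be shown, the completion rule and maximum must change, and recruitment rises about fourfold.

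If any attrition allowance lies behind the dyad count, it should be stated separately from the number randomized.

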5.3.2 Eligibility Criteria/Vulnerable Populations

Eligibility will be determined by treating physician, nurse practitioner, or research assistant involved in the care of the subject.

Inclusion criteria for patients will include:

1. Patient(s) over 18 years of age
2. Patient(s) capable of providing informed consent
3. Use or possible use of ICSI for oocyte insemination
4. At least 6 mature oocytes at time of insemination via ICSI

Exclusion criteria for patients:

1. Patient under 18 y/o
2. Patients not capable of providing informed consent
3. Use of IVF for insemination
4. Less than 6 mature oocytes at time of retrieval
5. Anonymous donor sperm source
6. Surgically retrieved sperm
7. Sperm sample not sufficient for use with ZyMot device

Inclusion criteria for donors:

1. Donor(s) over 18 years of age
2. Donor(s) capable of providing informed consent
3. Use of ejaculate sperm, fresh or frozen, for insemination
4. Sufficient sperm for use of ZyMot

Exclusion criteria for donors:

1. Anonymous donors

This study will not enroll vulnerable subjects; however, we routinely follow patients through their pregnancy to determine the outcome of embryo-transfer and will use the data from their standard of care follow-up calls for this study. The follow-up is considered minimal risk as it only involves data collection. No inducements, monetary or otherwise, will be offered to terminate a pregnancy. Individuals engaged in the research will have no part in any decisions as to the timing, method, or procedures used to terminate a pregnancy. Individuals engaged in the research will have no part in determining the viability of a neonate.

6 - Methods

6.1 Treatment – Device

6.1.1 Intended use for the device

The intended use for the ZyMot device is to separate sperm prior to ICSI insemination alongside and comparing it to sperm separation with use of density gradient.

6.1.2 Device administration and schedule

Patient/sperm source dyads enrolled in the study and meeting inclusion criteria will have their sperm sample prepared prior to, or near the time of, oocyte retrieval. Semen parameters will be recorded prior to separation. Semen will be split and separated via ZyMot and density gradient.

Density gradient will be performed as follows:

- Density gradient centrifugation will be performed using a one-layer preparation of 90% Isolate (Irvine Scientific) in 15 mL conical tubes. Semen will be layered over 1 mL of gradient and then centrifuged for 15 min at 300xg. The supernatant will be removed and discarded. The sperm pellet will be washed by mixing with Multipurpose Handling Medium Complete (Irvine Scientific) and centrifuging the sample for 5 min at 400xg. After the wash, the supernatant is removed and discarded and the pellet is re-suspended in culture medium (Continuous Single Culture-NX Complete, Irvine Scientific), assessed for sperm parameters, and held at room temperature until insemination.

ZyMot separation using the Multi (850 uL) microfluidic separation device will be performed as follows:

- 850 uL of untreated semen will be directly deposited into the inlet port of the ZyMot™ Multi device, followed by placement of 750 uL culture medium (Continuous Single Culture- NX complete, Irvine Scientific) in the outlet port and throughout the upper collection chamber. The device will then be incubated in a humidified 37C CO2 incubator for 30 minutes. During incubation, the healthiest and most motile sperm will swim through the microporous filter and into the upper collection chamber, where they will be recovered via the outlet port. 500 uL of the sperm sample will be removed and placed in a separate tube for analysis and insemination.
- After sperm processing, sperm parameters will be evaluated and recorded for each preparation, including sperm concentration, percent motility, and grade of forward progression. The density gradient preparation results will be recorded as Sample 1 in the electronic medical record (eMR) system gamete sheet. The ZyMot preparation results will be recorded as Sample 2 in the eMR system gamete sheet.
- Mode of oocyte insemination is ordered by the physician of record in the patient's chart. In the event that ICSI is ordered, the oocytes will be inseminated via ICSI. In the event that the physician orders ICSI per embryologist, the decision to perform ICSI will be a clinical decision based on the final prepared semen sample and/or other relevant clinical data. The sample must meet the following minimal criteria below in order to be eligible for IVF:

Parameters	Initial Sample	Final Sample
Volume	≥ 1.0 mL	≥ 0.25 mL
Concentration	≥ 15 mil/mL	NA
Motility	≥ 35%	≥ 70%
Forward Progression	≥ 2	≥ 3

- In the event that any of the parameters above are not met and/or other clinical parameters favoring ICSI insemination over IVF including, but not limited to, microscopic appearance of the oocytes, review of previous insemination cycles, and previous morphology grading of sperm, ICSI will be performed.
- In the event that the parameters above are met and there are not any other factors favoring ICSI insemination, the oocytes will be inseminated via IVF from sperm separated by density

gradient and the oocytes will not be inseminated via ZyMot separated sperm, however, the pre and post sperm parameters following ZyMot separated sperm and density gradient separated sperm will be recorded as per our secondary objectives. Similarly, in the event that there are less than 6 mature oocytes, the oocytes will only be inseminated via density gradient separated sperm, however, pre and post sperm parameters following ZyMot separated sperm and density gradient separated sperm will be recorded as per our secondary objectives.

- As per our standard verbal and written consenting protocols, patients are aware that their oocytes may undergo ICSI the day of oocyte retrieval based on above criteria. The decision to perform ICSI will not be affected in any way by enrollment into this study.
- Following oocyte retrieval, oocytes will be denuded of their cumulus cells per standard protocol. If at least 6 mature oocytes (determined by visualization of a polar body) are present, half the oocytes will be ICSI inseminated with sperm prepared via ZyMot device and half will be ICSI inseminated with sperm prepared with density gradient. Patients whose patient identification number (PID) is even will have the group of oocytes inseminated with sperm separated via ZyMot device recorded first in the eMR gamete sheet (beginning with oocyte #1.) Patients with an odd PID will have the oocytes inseminated with sperm separated via density gradient recorded first in the eMR gamete sheet (beginning with oocyte #1.) In the event of an odd number of oocytes, the patients with even PIDs will have the extra oocyte inseminated with sperm separated via Zymot device and patients with odd PIDs will have the extra oocyte inseminated with sperm separated via density gradient. Inseminated oocytes will be grouped into separate wells of a LifeGlobal 4 well GPS dish (Cooper Surgical) by the sperm separation method — one well will contain all oocytes inseminated with sperm selected by ZyMot device and a separate well will contain all oocytes inseminated with sperm selected by density gradient centrifugation.

Control Group of Oocytes:

Half of the eggs will be inseminated via ICSI using sperm selected by conventional gradient centrifugation.

Treatment Group of Oocytes:

- Half of the eggs will be inseminated via ICSI using sperm selected using ZyMot.
- Fertilization assessment will be performed between 16 and 18 hours after insemination and normal fertilization will be considered visualization of exactly two pronuclei. Normally fertilized oocytes (embryos) will then be cultured in Continuous Single Culture Medium — NX Complete (Irvine Scientific) in separate, numbered droplets in LifeGlobal microdrop GPS dishes (Cooper Surgical.) The numbers of the droplets will correlate to oocyte/embryo number in the eMR gamete sheet and, thereby, also correlate to the type of sperm used for the insemination. Development of the embryos will be assessed on culture days 5 and 6 and embryo stage and grade will be recorded for each embryo.
- Decision as to which embryo to transfer will be made by the clinical team irrespective of type of sperm preparation for insemination. Transfer of embryo is generally based on ploidy status (if PGT-A was performed) or blastocyst grade (if PGT-A was not performed). In the event that two embryos of similar quality are available for transfer, priority is given to lowest embryo number (correlated to oocyte/embryo number). The decision as to which embryo to transfer will be made regardless of whether the sperm used to inseminate the oocyte was processed with density gradient or ZyMot and will be as per our standard protocol.

6.1.3 Method of Assignment/Randomization

Patient/sperm source dyads meeting inclusion criteria and enrolled in the study will have their sperm sample prepared prior to or near the time of oocyte retrieval. Semen parameters will be recorded prior to separation. Semen will be split and separated via ZyMot and density gradient.

Following oocyte retrieval, oocytes will be denuded of their cumulus cells per standard protocol. If at least 6 mature oocytes (determined by visualization of a polar body) are present, half the oocytes will

be ICSI inseminated with sperm separated via ZyMot device and half will be ICSI inseminated with sperm prepared with density gradient. Patients whose patient identification number (PID) is even will have the group of oocytes inseminated with sperm separated via ZyMot device recorded first in the eMR gamete sheet (beginning with oocyte #1.) Patients with an odd PID will have the oocytes inseminated with sperm separated via density gradient recorded first in the eMR gamete sheet (beginning with oocyte #1.) In the event of an odd number of oocytes, the patients with even PIDs will have the extra oocyte inseminated with sperm separated via Zymot device and patients with odd PIDs will have the extra oocyte inseminated with sperm separated via density gradient.

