The study will be completed once 408 oocytes are randomized, which is anticipated to be in approximately 1-2 years.

Study Design

Subjects meeting inclusion criteria will be approached for inclusion into the study and informed consent will be obtained from the patient and the sperm source. Controlled ovarian hyperstimulation will be performed followed by oocyte retrieval as per our standard protocol. On the day of oocyte retrieval, sperm samples will be split into two samples and processed via density gradient (our standard sperm separation technique) and ZyMot (our experimental arm). Sperm parameters will be evaluated pre and post-sperm separation following ZyMot and density gradient. Following oocyte retrieval, the oocytes will be assessed as per our standard fashion. In the event that the oocytes will be inseminated via intracytoplasmic sperm injection (ICSI) and there are 6 or more mature oocytes, half of the oocytes will be inseminated via ZyMot processed sperm and half with sperm processed via density gradient. In the event that there are less than 6 mature oocytes or the insemination technique will be IVF, the oocytes will only be inseminated with sperm processed via density gradient. Additionally, in the event that the sperm sample is insufficient for ZyMot processing (<0.5 million total motile sperm and/or no sperm observed with progressive forward motility), the sperm will not be processed with ZyMot and the patient will be withdrawn from the study.

The primary outcome will be percentage of good quality embryo formation resulting from oocytes inseminated following ZyMot separated sperm compared to density gradient separated sperm. Secondary outcomes will include percentage of euploid embryos in the

event that PGT-A is performed, pregnancy rates, miscarriage rates, live birth rates, and sperm parameters following sperm processing. Decision to transfer an embryo will be made as per our standard protocols regardless of the sperm processing technique.

Study Population

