5.1 General Design Description

This study will be a randomized sister oocyte (oocytes from the same patient within the same cycle) study at a single academic institution. By randomizing sister oocytes, we will eliminate any potential confounding variables.

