6.3.1 Study Schedule

Subject time devoted to this study will be the reviewing and signing the informed consent.

The timepoints for involvement in the study will be:

1. The process of informed consent for patient/sperm source dyads
2. The oocyte retrieval- After retrieval in the event that there are 6 or more mature oocytes, the couple will be enrolled into the study
3. The sperm separation- The sample will either be obtained via fresh production from sperm source the day of oocyte retrieval or will be cryopreserved sperm. The sample will be assessed the day of oocyte retrieval and if the sperm sample is sufficient, it will be processed via ZyMot and density gradient. Following processing of the sperm sample, in the event that there are 6 mature oocytes available to inseminate, the patient will be enrolled into the study. Oocytes will be randomized to insemination via density gradient separated sperm and ZyMot separated sperm.
4. In the event that the orders were written for ICSI per embryologist, if the patient does not meet criteria for IVF the day of oocyte retrieval (as per section 6.3), the oocytes will be inseminated via IVF with density separated sperm only, however, the pre and post sperm parameters following ZyMot separated sperm and density gradient separated sperm will be recorded as per our secondary objectives. Similarly, in the event that there are less than 6 mature oocytes, the oocytes will only be inseminated via density gradient separated sperm, however, pre and post sperm parameters following ZyMot separated sperm and density gradient separated sperm will be recorded as per our secondary objectives. Insemination- Following oocyte retrieval, those enrolled into the study will have their oocytes split and inseminated with ZyMot separated sperm and density gradient separated sperm.
5. Fertilization check- Approximately 16-18 hours following insemination the embryos will be assessed for fertilization.
6. Five and 6 days following insemination, the embryos will be assessed for stage of growth and those reaching blastocyst stage will be given a morphological grade.
7. In the event that patient will undergo a fresh transfer the patient will be transferred 5 days following oocyte retrieval. In the event that pre-implantation genetic testing is performed or the embryos are cryopreserved for any other reason, the patient may undergo a frozen embryo transfer in standard fashion.

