6.3.4 Recruitment, Enrollment and Retention

Recruitment into the study will be performed by a study investigator at NYU Langone RSOFNY. Patient/sperm source dyads are recruited from the study investigators' practice (RSOFNY) during a routine clinical visit. If patient/sperm source dyads desire to enroll in the study, it will be denoted in their medical record chart. If they meet eligibility criteria on the day of oocyte retrieval (no evidence of severe male factor infertility or surgically derived sperm, at least 6 mature oocytes available for randomization, and possibility for ICSI insemination) the study will be performed as per study protocol.

In the event that the patient consented to the study but the provided semen sample on the day of oocyte retrieval shows severe male factor infertility. The patient/sperm source dyad will then be withdrawn from the study since the sample will not qualify for preparation via ZyMot nor density gradient.

In the event that the patient/sperm source dyad consented to the study but does not meet the inclusion criteria of ICSI insemination or at least 6 mature oocytes available for insemination, insemination will occur only with the sperm separated via density gradient, however, the sperm parameters following ZyMot and density gradient sperm separation will be recorded. The data on sperm parameters after sperm separation via ZyMot and density gradient will still be collected but the patient/sperm source dyad will have no further participation in the study.

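### The oocytes are called randomized, but the only stated assignment rule is PID parity, which is not a chance mechanism

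*Combined protocol and SAP*

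**What the plan says.** Nine places describe the oocytes as randomized or as awaiting randomization:

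- Synopsis, Study Duration: "The study will be completed once 408 oocytes are randomized"
- Synopsis, Number of Participants: "408 oocytes will be needed to randomize"
- 5.1, which also draws the consequence: "By randomizing sister oocytes, we will eliminate any potential confounding variables"
- 5.3.1: "As this study will be randomizing oocytes"
- 6.3.1: "Oocytes will be randomized to insemination via density gradient separated sperm and ZyMot separated sperm"
- 6.3.4: "at least 6 mature oocytes available for randomization"
- 6.4.2, 6.4.4 and 7.15, in similar words. Section 6.4.4 is more cautious than 5.1 and claims only that the influence of confounders is limited.

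The method stands in 6.1.3 and is repeated in 6.1.2. It has three parts. With at least 6 mature oocytes, half go to each sperm preparation. "Patients whose patient identification number (PID) is even will have the group of oocytes inseminated with sperm separated via ZyMot device recorded first" in the gamete sheet, starting at oocyte 1, and odd PIDs have the density gradient group first. When the count is odd, the extra oocyte goes to ZyMot for an even PID and to density gradient for an odd one.

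On assessment, 6.1.2 keeps the arms in separate wells after ICSI. It then moves normally fertilized oocytes to droplets whose numbers can be traced to the sperm preparation. Section 6.3.1 says that "those reaching blastocyst stage will be given a morphological grade", and 5.2.1 defines the primary endpoint as a day 5 or 6 blastocyst graded good or fair.

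**The concern.** A split within one patient's cohort removes differences between patients. It does not by itself balance the oocytes within a patient. That balance comes from how the cohort is divided, and the claim in 5.1 rests on that step. The plan gives no random sequence, no tool and no concealment, and it does not say how individual mature oocytes are sorted into the two halves. The oocytes have been denuded and inspected for maturity by then, so staff can see them.

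If the better-looking oocytes tended to go to one arm, the comparison of good-quality embryo rates would mix oocyte quality with sperm preparation, and no analysis in 6.4.3 could separate the two. The division cannot be repaired after insemination. A second and separate route is the grading of blastocysts by someone who could know the arm. Random allocation would not close that route.

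**Working it through.** **1. The plan's own figure.** Section 6.4.2 gives n = 16pq(1 − r)/d². The inputs are 48% and 55%, so p = (0.48 + 0.55)/2 = 0.515, q = 0.485, d = 0.07, with r = 0.5. Then n = 16 × 0.515 × 0.485 × 0.5 / 0.0049 = 407.8, rounded up to 408. This reproduces. At 6 oocytes per cycle, 408/6 = 68 cycles; at the average of 12 given in 5.3.1, 408/12 = 34. How oocytes are allocated does not enter the formula, so random allocation leaves 408 unchanged.

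**2. The claim against the rule.** Six oocytes can be halved in C(6,3) = 20 ways and twelve in C(12,6) = 924 ways. The plan states no chance mechanism for choosing among them. Two readings are possible.

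- *Literal.* Parity sets which already-formed group is recorded first, and which arm gets an odd extra oocyte. How the groups were formed is then unspecified, and the choice is left to staff who can see the oocytes.
- *Block.* Oocytes are numbered and parity gives the first block to one arm. This is systematic allocation by an identifier known before the oocytes are numbered.

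**3. Size under the block reading, numbering independent of parity.** Suppose the first block differs from the second by e percentage points in good-quality yield. Assume equal-sized cycles and half of PIDs even. Each cycle then adds +e or −e to the ZyMot minus density gradient difference with equal chance. The mean over n cycles has expectation 0 and SD e/√n:

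- n = 34: 0.171e
- n = 68: 0.121e

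The documents do not give e. For an assumed e of 5 points the SD is 0.86 (34 cycles) or 0.61 (68 cycles). For e = 10 it is 1.7 or 1.2. Against a 7-point target this is minor.

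**4. Where the averaging fails.** If whoever numbers the oocytes does so with parity in mind, the sign no longer alternates by chance. If it were the same in every cycle, the mean would be e itself, whatever n is. Under the literal reading there is not even a stated block to alternate. Neither case can be bounded from the documents.

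**5. How much bias would matter.** This step is illustrative, and the bias b is assumed. Take no true effect, 48% in both arms, r = 0.5, and a shift b in one arm. Let p = 0.48 + b/2, v = 2p(1 − p)(1 − r), s0 = √(v/N), s1 = √((v − b²)/N). The chance of two-sided p < 0.05 is Φ((b − 1.96 s0)/s1) + Φ((−b − 1.96 s0)/s1). For b = 0.02 and N = 204: v = 0.2499, s0 = 0.0350, s1 = 0.0350, giving 0.088. Both counts of pairs are shown, because whether 408 means oocytes or pairs is a separate question.

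| Assumed bias | 204 pairs | 408 pairs |
|---|---|---|
| 0 points | 5% | 5% |
| 2 points | 9% | 13% |
| 3 points | 14% | 23% |
| 5 points | 30% | 52% |

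A bias well below the 7-point target would already distort the test.

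**6. Grading.** The endpoint depends on an assigned grade (5.2.1), and the droplet number leads back to the arm (6.1.2). No section says who grades, what that person sees, or whether anyone is masked. The statement in 6.1.2 that sperm preparation plays no part concerns the choice of embryo for transfer, not grading.

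**The case against.** The strongest reply is that the block reading is the natural one. Section 6.1.3 is headed as the assignment method, starts at oocyte 1, and uses the same parity to place an extra oocyte. On that reading order effects roughly cancel across even and odd PIDs, the sibling design has already dealt with patient factors, and step 3 shows that little is left. Nothing in the plan suggests that oocytes are numbered with parity in mind.

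Most of this stands, and it limits how large the problem is likely to be. It does not supply a chance mechanism. It also needs numbering to be independent of parity, which the plan does not ensure, and the literal wording does not commit to the block reading at all.

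A reader might go further and infer three things that the documents do not support:

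- *That staff do select oocytes by arm.* No section says so; the plan only fails to prevent it.
- *That grading is open, or that biased grading could account for the whole target difference.* The plan is silent on what the grader sees. It also does not give the share of oocytes that reach blastocyst, so no bound can be derived.
- *That the statement on confounding in 6.4.4 is wrong as well.* Limiting confounding follows from the sibling design alone. Only the word for randomizing is unsupported there.

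**Conclusion.** The randomization label and the claim in 5.1 to eliminate confounding are not supported by the rule that the plan states. Confidence in this is high, because it rests on the text: parity is deterministic, known in advance, and on a literal reading does not divide the oocytes at all. What is unprotected is balance between oocytes of the same patient; differences between patients are still removed.

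The size and direction of any bias are unknown. Under block allocation with independent numbering and equal-sized cycles it is a mean-zero imbalance with SD 0.12e to 0.17e, which is minor. Under the literal reading, or with numbering that depends on parity, it cannot be bounded. The error rates in step 5 show sensitivity to assumed bias and are not evidence that bias exists.

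The absence of stated masking is a secondary point. It is an omission in the plan, not a finding that grading is unmasked. The allocation point carries the recommendation.

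**What to change.** In 6.1.2 and 6.1.3, replace the parity rule. Place the mature oocytes in numbered positions first, and only then reveal the next computer-generated list for that cycle, prepared in advance. The list should do three things:

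- assign half the positions to each arm;
- randomize the arm of any extra oocyte;
- randomize which arm is recorded first in the gamete sheet, so that recording order does not lose the alternation that parity gave it.

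The cost is a short amendment, one list per cycle (34 cycles at 12 oocytes to 68 at 6), and modest laboratory work: numbered positions, following the list at ICSI, and labelling checks against mix-ups. The sample size does not change.

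If this is not adopted, describe the oocytes as allocated by PID parity in the nine places listed and in the heading of 6.1.3, and state there how the two halves are formed. In 5.1, replace the claim to eliminate confounding with a statement that differences between patients are removed. Section 6.4.4 may keep its claim to limit confounding.

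On grading, state who assigns stage and grade. Where existing staff allow, have both recorded before the arm key is viewed; otherwise state that grading is unmasked. The documents give no staffing information, so feasibility is for the site to judge.
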